Patients with PD by RECIST 1.1 (unconfirmed and confirmed) who, in the Investigator's opinion, continue to receive benefit from their treatment and who meet the criteria for treatment in the setting of PD may continue to receive treatment for as long as they are gaining clinical benefit.

However, patients will not be permitted to continue immunotherapy if progression occurs after confirmed response (complete response [CR] or partial response [PR] as defined by RECIST 1.1) to immunotherapy treatment in target lesions (regardless of the appearance of new lesions), ie, the response and progression events both occurred in the target lesions while receiving immunotherapy during the same treatment period.

Patients in Modules with combination durvalumab + tremelimumab may restart treatment with the combination if they complete the 4 dosing cycles with durvalumab + tremelimumab (with clinical benefit per Investigator judgement) but subsequently have PD during treatment with durvalumab alone and provided they meet eligibility criteria for retreatment.

See Section 7.8 for post-study access to treatment information.

[figure not shown]
^{*} Where treatment is discontinued due to progressive disease, it is recommended that a confirmatory scan be performed prior to discontinuation to verify progression. According to RECIST 1.1 modified for confirmation of progression, a confirmatory scan is required following an overall time point assessment of progression (PD), no earlier than 4 weeks after the previous assessment of PD.

Follow up of patients post discontinuation of study drug

Patients who have discontinued treatment due to toxicity or symptomatic deterioration, clinical progression, or withdrawal from treatment, or patients who have started a subsequent anticancer therapy, will have one additional tumor assessment on a subsequent scan, if clinically feasible, will be followed up for AEs for 90 days, and thereafter followed up for survival (described in the next section). These patients are not eligible for re-treatment at any time.

Follow Up for Safety and Survival

Patients will attend a safety follow up visit 90 days after study treatment discontinuation. Thereafter, patients will be contacted by phone or email every 3 months for survival status until the final DCO.

Tumor specific modules (APPENDIX F) detail which treatment regimen, combination therapy or monotherapy, will be used.

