An individual patient will not receive any further IP treatment (durvalumab + tremelimumab combination therapy, durvalumab monotherapy) if any of the following occur in the patient in question:

- 1 Withdrawal of consent from further treatment with IP. The patient is, at any time, free to discontinue treatment, without prejudice to further treatment. A patient who discontinues treatment is normally expected to continue to participate in the study unless they specifically withdraw their consent to further participation in any study procedures and assessments (see Section 3.10.2)
- 2 An AE that, in the opinion of the Investigator or AstraZeneca, contraindicates further dosing
- 3. Any AE that meets criteria for discontinuation as defined in the Dose Modification and Toxicity Management Guidelines (see Section 6.9.1)

- 4. Pregnancy or intent to become pregnant
- 5. Non-compliance with the study protocol that, in the opinion of the Investigator or AstraZeneca, warrants withdrawal from treatment with IP (eg, refusal to adhere to scheduled visits)
- 6. Initiation of alternative anticancer therapy including another investigational agent
- 7. Clinical progression, ie, Investigator determination that the patient is no longer benefiting from treatment with IP, with or without radiological progression by RECIST 1.1
- 8. Transition to commercial drug supply. Note: If allowed by local regulations, the study Sponsor may transition patients from study treatment to commercial drug supply when the IP becomes commercially available in the country where the patient is living. See Section 7.8 for post-study access to treatment information.

Unless they withdraw consent for further follow up, patients who discontinue study therapy will continue on study for acquisition of safety information through 90 days after the last dose of study treatment, and for further collection of information regarding survival until the final DCO.

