4.3 Follow up period

Procedures will be performed according to the Study Plan.

All patients who discontinue study treatment will attend a safety follow up visit 90 days after study treatment discontinuation.

The following procedures will be performed:

- 1. Assess AEs.
- 2. Update concomitant medications.
- 3. Record Investigator assessment of treatment response.
- 4. Record subsequent therapy.
- 5. Record survival status.

After this safety follow up visit, patients will be contacted by phone or email every 3 months to check survival status until death or final DCO, whichever occurs first.

Patients who do not discontinue treatment before the final DCO will continue to be followed after the final DCO, as indicated in Section 6.3.12.

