3.3.2.1 Objective response

Objective response (using Investigator assessments) is defined as at least 1 visit response of CR or PR. Data obtained up until progression, or the last evaluable assessment in the absence of progression, will be included in the assessment of objective response. Patients who go off treatment without progression, receive a subsequent therapy, and then respond will not be considered responders.

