3.3.2.2 Disease control rate

Disease control at 6 or 12 months is defined as a best objective response (BoR) of CR or PR or stable disease (SD) as assessed by the investigator, in the first 6 or 12 months, respectively, following the start of study treatment.

Disease control will be determined based on the Investigator assessments and all data up until the first confirmed progression event. This will use all data up until the progression event that is used for the analysis (ie, unconfirmed progressions are not considered progression events, which means that the BoR that contributes to the assessment of disease control may be after an unconfirmed progression for some patients). Patients who go off treatment without progression, receive a subsequent therapy, and then respond will not be considered responders.

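### SAP 3.3.2.2 has no explicit cut at the start of subsequent anticancer therapy for stable disease, so stable disease first seen on the next drug can count as disease control

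*SAP*

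**What the plan says.** SAP 3.3.2.2 defines disease control as a best response of CR, PR or SD, by investigator assessment, in the first 6 or 12 months from the start of study treatment. On which data count, it says: "Disease control will be determined based on the Investigator assessments and all data up until the first confirmed progression event". It adds that "unconfirmed progressions are not considered progression events", so a best response recorded after an unconfirmed PD still counts.

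On later drugs there is one sentence: "Patients who go off treatment without progression, receive a subsequent therapy, and then respond will not be considered responders". The identical sentence stands in SAP 3.3.2.1, where the endpoint contains no SD: "Objective response (using Investigator assessments) is defined as at least 1 visit response of CR or PR".

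Under SAP 4.2.2 the denominator for ORR and DCR is the patients who have an assessment in the period, not all dosed patients.

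The protocol lets assessments made after a switch reach the data. Section 1.4 provides that "patients who have started a subsequent anticancer therapy, will have one additional tumor assessment on a subsequent scan", if clinically feasible. Section 4.3 lists "Record Investigator assessment of treatment response" and the recording of subsequent therapy among the procedures at the 90-day visit. Protocol 7.2.1 and SAP 1.2 follow such patients to confirmed progression.

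**The concern.** SD is what separates DCR from ORR, and it is the one category the safeguard does not name. The sentence does its work under ORR. Carried unchanged into the disease control section, it leaves open whether SD reached on another drug is credited to study treatment.

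The SAP takes care over this elsewhere. In 4.2.1 (Laboratory assessments; Assessment of Thyrotoxicity) data are cut at the first subsequent therapy, and the laboratory text gives the reason: toxicities within the 90 days may belong to the later drug. The same reasoning applies to tumour status.

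At stake is an exploratory endpoint, but one reported with exact confidence intervals and across nine subgroup factors. SAP 4.1 says that descriptive efficacy data may be used as supporting evidence for health authorities. Two programmers could derive different DCRs from the same data.

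**Working it through.** **Plan's own figures.** The documents give no expected DCR, so there is none to reproduce. The one design probability in SAP 1.3 (over 75% for at least ten events at 1% incidence, N = 1200) reproduces: the exact binomial tail is 0.759. The Clopper-Pearson intervals in Table 1 at N = 1200 also reproduce: 17.8-22.4% at 20% and 47.1-52.9% at 50%. The same interval method is used below.

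**Who is affected.** Best response is a best-ever measure. A patient already rated CR, PR or SD on study treatment counts with or without a cut. That leaves two groups:

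- *Group A*: assessed on treatment with no CR, PR or SD (for example only unconfirmed PD), then a new drug, then SD within the window and before confirmed PD.
- *Group B*: no on-treatment scan, then a new drug, then a first assessment within the window.

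**Can these patients arise?** Under Protocol 3.9, treatment ends on "Initiation of alternative anticancer therapy including another investigational agent". It also ends on clinical progression, with or without radiological progression. A scan confirming PD before stopping is recommended. Switching without confirmed PD is therefore foreseeable.

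**Does the safeguard catch Group A?** There are two ways to read its condition of no progression:

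- If it uses the section's own meaning (confirmed only), the patient meets the condition, but SD is not plainly a response, so SD counts.
- If it means no PD of any kind, the sentence does not reach this patient at all, and even CR or PR on the next drug would count.

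**Group A, size on assumptions.** Let D be DCR with a cut, f the share of uncontrolled patients who switch before confirmed PD and are scanned in the window, and s the share of those rated SD. None of these is in the documents. The denominator does not change, so the shift is (1 − D) × f × s.

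| D | f | s | Shift in points |
|---|---|---|---|
| 50% | 2% | 30% | 0.50 × 0.02 × 0.30 = 0.3 |
| 35% | 5% | 50% | 0.65 × 0.05 × 0.50 = 1.6 |
| 20% | 10% | 50% | 0.80 × 0.10 × 0.50 = 4.0 |

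Middle row at N = 1200: 420 patients are controlled with the cut, 35.0% (95% CI 32.3-37.8). Of the other 780, 5% is 39, and half of those is 19.5, rounded to 20. Without the cut, 440/1200 = 36.7% (33.9-39.5). The shift of 1.7 points is more than half of the interval's half-width, (37.8 − 32.3)/2 = 2.75.

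**Group B, size on assumptions.** Let m be these patients as a share of those assessed before any switch. They enter the denominator too, so DCR becomes (D + m × s)/(1 + m), and the shift is m × (s − D)/(1 + m).

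- D = 20%, m = 10%, s = 50%: (20 + 5)/1.10 = 22.7%, a shift of +2.7 points.
- D = 50%, m = 10%, s = 20%: (50 + 2)/1.10 = 47.3%, a shift of −2.7 points.
- s = D: no shift.

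Over D 20-50%, m 2-10% and s 20-50%, the shift runs from −2.7 to +2.7 points.

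**The case against.** The strongest reply is that the sentence stands inside the disease control section, where *respond* can reasonably mean reaching that section's endpoint, SD included; on a CR/PR reading it does little there. That reading is possible. But the SAP does not state it, the wording is identical to the ORR text, and the laboratory section shows how an explicit cut is written.

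Second, the protocol footnote that recommends a scan before stopping also says that a confirmatory scan is required after PD. This should make Group A smaller. It does not empty it, since patients can stop for clinical progression or change drug first.

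Third, post-discontinuation scans may be few. Protocol 1.4 makes the extra scan conditional on feasibility, and Protocol 5.1 says that no further efficacy assessments will be performed. This stands as a limit on size, and it conflicts with Protocol 7.2.1 and SAP 1.2.

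A reader might also infer that DCR is definitely inflated, that the error runs in one direction only, or that each percent of switchers adds a full point. The documents support none of these. Patients with disease control on study treatment are untouched, Group B can lower DCR through the denominator, and the last inference needs every such patient to be uncontrolled beforehand and then rated SD.

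**Conclusion.** The gap is real on a literal reading: SD first recorded after the start of another anticancer drug, and before confirmed PD, counts as disease control. DCR can therefore be biased, upward through Group A and in either direction through Group B. The true size cannot be computed, because the documents give no rate of switching, of scanning after a switch, or of SD on the next drug. On the assumptions above, the shift is about 0.3 to 4 points for Group A and −2.7 to +2.7 points for Group B.

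DCR is exploratory and descriptive, with no hypothesis test. The primary AESI endpoint, OS and the sample size are unaffected. The point is worth correcting because it is cheap to close and the result may be shown to health authorities.

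**What to change.** In SAP 3.3.2.2, state that only assessments up to the first confirmed progression or the start of subsequent anticancer therapy, whichever is first, contribute to best response, for CR, PR and SD alike. Add the same therapy cut to 3.3.2.1 for consistency; that section already excludes later CR and PR.

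In SAP 4.2.2, apply the same cut when deciding who has an assessment in the period. Patients first assessed after switching then leave both numerator and denominator. Counting them as not controlled would be a separate analysis choice that contradicts the stated denominator, and it is not proposed here.

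Reconcile the texts on tumour assessment after discontinuation: Protocol Synopsis, 1.4, 5.1 and 7.2.1, and SAP 1.2.

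The cost is a few sentences. The laboratory cut already needs the start date of subsequent therapy. Protocol 4.3 lists subsequent therapy only among the 90-day procedures, so if later scans are to be used, check that therapy started after that visit is dated. DCR may come out slightly lower, and a few patients may leave the denominator.

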3.4 Baseline

3.4.1 Prior and concomitant medications

The WHO Drug B3 dictionary will be used for concomitant medication coding.

Any medications taken by the patient prior to the first dose date of study treatment will be considered prior medication.

Any medication taken by the patient at any time after the date of the first dose (including the date of the first dose) of study treatment up to 90 days after last dose will be considered concomitant medication. Any medication that started prior to the first dose of study treatment and ended after the first dose or is ongoing will be considered as both prior and concomitant medication.

For the purpose of inclusion in prior or concomitant mediation summaries, incomplete medication start and stop dates will be imputed as detailed in Section 3.1.3.

4. ANALYSIS METHODS

4.1 General principles

No hypothesis testing is planned for this single arm study. Each module will be summarised separately.

The general principles as mentioned below will be followed throughout the study:

- Descriptive statistics will be used for all variables, as appropriate, and will be presented separately for each module. Descriptive safety and efficacy data from the STRONG study may be utilized as supporting evidence for health authority considerations.
- Continuous variables will be summarized by the number of observations, mean, standard
 deviation, median, minimum, and maximum. For log transformed data it is more
 appropriate to present geometric mean, coefficient of variation (CV), median, minimum
 and maximum. Categorical variables will be summarized by frequency counts and
 percentages for each category.
- Unless otherwise stated, percentages will be calculated out of the population total.
- Exact CIs for proportions will be calculated using the Clopper-Pearson method.
- For percentiles of survival times based on the Kaplan-Meier method (eg, median survival), CIs will be calculated using the default method available in the SAS LIFETEST procedure (ie, the Klein and Moeschberger extension of the Brookmeyer-Crowley method).
- For point-estimates of survival based on the Kaplan-Meier method (eg, for OS at 12 months), CIs will be calculated using the default method available in the SAS LIFETEST procedure (ie, using Greenwood's estimate of standard error and a log-log transformation).
- For continuous data the mean and median will be rounded to 1 additional decimal place compared to the original data. The standard deviation will be rounded to 2 additional decimal places compared to the original data. Minimum and maximum will be displayed with the same accuracy as the original data.
- For categorical data, percentages will be rounded to 1 decimal place.
- SAS® version 9.3 or higher will be used for all analyses.

Baseline will be the last assessment of the variable under consideration prior to the intake of the first dose of study treatment.

All data collected will be listed.

4.2 Analysis methods

As this is a single arm study, no endpoints are to be subjected to formal statistical analysis.

4.2.1 Safety data

Data from all cycles of treatment will be combined in the presentation of safety data. The following sections describe the planned safety summaries. However, additional safety tables may be required to aid interpretation.

Adverse Events

All AEs will be summarised descriptively, in terms of number of patients (n) and percentage of patients (%) reporting the event by MedDRA system organ class (SOC) and preferred term (PT). The majority of the AE summaries, unless stated otherwise, will be based on TEAEs.

Any adverse events that occur prior to dosing or starting more than 90 days after discontinuing treatment will be presented in a separate summary by SOC and PT.

All reported AEs will be listed along with the date of onset, date of resolution (if AE is resolved) and investigator's assessment of severity and relationship to study drug.

Summary information (the number and percent of patients by SOC and PT) will be tabulated for:

- All TEAEs
- All TEAEs causally related to study medication (as determined by the reporting investigator)
- TEAEs with CTCAE grade 3 or higher
- TEAEs with CTCAE grade 3 or higher, causally related to study medication (as determined by the reporting investigator)
- TEAEs by outcome
- TEAEs with outcome of death
- TEAEs with outcome of death causally related to study medication (as determined by the reporting investigator)
- All treatment-emergent SAEs
- All treatment-emergent SAEs causally related to study medication (as determined by the reporting investigator)
- All treatment-emergent SAEs by maximum NCI CTCAE grade
- TEAEs leading to discontinuation of study medication
- TEAEs leading to discontinuation of study medication, causally related to study medication (as determined by the reporting investigator)
- TEAEs leading to hospitalization
- TEAEs leading to dose interruption of study medication
- Other significant TEAEs
- Other significant TEAEs causally related to study medication (as determined by the reporting investigator)
- Designated medical events
- Infusion reaction TEAEs (as determined by the reporting investigator)

As well as the overall summary of the number and percentage of patients in each SOC/PT category, an overall summary of the number of episodes in each SOC/PT category will be presented. In addition, a truncated AE table of most common AEs and another table showing most common AEs with CTCAE grade 3 or higher, showing all events that occur in at least 5% of patients overall will be summarised by PT, by decreasing frequency. This cut-off may be modified after review of the data. When applying a cut-off (ie, x %), the raw percentage

will be compared to the cut-off, no rounding will be applied first (i.e., an AE with frequency of 4.9% will not appear if a cut-off is 5%).

An overall summary of the number and percentage of patients in each AE category (Any AE, Any AE causally related to treatment, Any AE of CTCAE grade 3 or higher etc...) will be presented.

Each AE event rate (per 100 patient years) will also be summarised by PT within each SOC for the output summarising all AEs. For each preferred term, the event rate is defined as the number of patients with that AE divided by the total drug exposure of patients at risk of AE. The denominator is the total duration of treatment (in years) across all patients calculated as the sum total (of all patients) of days from first dose to the earlier of the date of first onset of the event or the last day of study medication.

As a part of the trial's Disclosure Record to the National Institute of Health (NIH), the following tables will be produced

- TE non-serious AEs
- TE non-serious AEs causally related to study medication (as determined by the reporting investigator)
- TE non-serious AEs occurring in >5% of Patients
- TE non-serious AEs occurring in >5% of patients causally related to study medication (as determined by the reporting investigator)
- Summary of the number of episodes of treatment-emergent SAE in each SOC/PT category
- Number of subjects enrolled per age group as per EU categories.

Fluctuations observed in CTCAE grades during study will be listed for those TEAEs which are CTCAE > 3.

In addition, all AEs will be listed.

Adverse events of special interest (primary outcome)

Summaries of treatment emergent AESI by category and PT will include number (n) and percentage (%) of patients who have:

- At least one treatment-emergent AESI
- At least one treatment-emergent AESI by outcome
- At least one treatment-emergent AESI leading to treatment interruption or discontinuation
- At least one treatment-emergent serious AESI
- At least one treatment-emergent AESI by maximum NCI CTCAE grade
- At least one treatment-emergent AESI causally related to study medication
- At least one treatment-emergent AESI with fatal outcome
- At least one treatment-emergent AESI which required additional treatment with steroids, immunosuppressants and hormone replacement therapy
- Laboratory findings, vital signs and other safety parameters associated with AESI will be summarised as part of the AESI outcome measures.

Length of intervention with steroids, immunosuppressants and/or hormone replacement therapy for AESIs will be calculated based on treatment start and stop dates. Total treatment

times will then be combined for each patient and summarised for patients experiencing at least one treatment-emergent AESI.

The exact 95% CIs around the incidence estimates will also be reported for each AESI type.

A summary of total duration (days) of AESI will be provided. For ongoing AESI, the date of death or data cut-off will be imputed as end date.

Immuno-mediated adverse events

Summaries of treatment-emergent imAEs by AESI category and PT will include number (n) and percentage (%) of patients who have:

- At least one treatment-emergent imAE
- At least one treatment-emergent imAE by outcome
- At least one treatment-emergent imAE leading to treatment interruption or discontinuation
- At least one treatment-emergent serious imAEs
- At least one treatment-emergent imAE by maximum NCI CTCAE grade
- At least one treatment-emergent imAE causally related to study medication
- At least one treatment-emergent imAE with fatal outcome

Subgroup analyses

Subgroup analyses will be conducted for the summary of TEAEs in the following subgroups of the SS:

- Sex (male versus female)
- Age at baseline: <65 vs 65-74 vs ≥75 years of age). This will be determined from the date of birth (BRTHDAT in the DM domain) and baseline visit (VIS_DAT in the VISIT domain) on the eCRF. Patients with a partial date of birth (ie for those countries where year of birth only is given) will have an assumed date of birth of 1st Jan [given year]). Patients with a missing age value will be included using the mean age and categorised accordingly.
- Race: Asian vs non-Asian
- ECOG performance status at baseline: 0-1 vs 2
- Tumor histology: Urothelial (i.e. TCC) vs non-urothelial
- PDL1: high >=25% vs low <25%. If data is available from the central laboratory, the central laboratory result will be used in the group derivation, otherwise, the local test result will be used.

Subgroup analyses will also be conducted for the summary of OS, ORR and DCR in the following subgroups of the SS:

- Age at baseline: <65 vs 65-74 vs ≥ 75 years of age
- ECOG performance status at baseline: 0-1 vs 2
- Primary tumor location: Bladder vs Renal pelvis and Ureter vs Urethra vs Other
- Stage: III vs IV
- Tumor histology: Urothelial (i.e. TCC) vs non-urothelial
- Previous platinum chemotherapy: platinum vs non-platinum chemotherapy
- Best response to previous therapy (CR vs PR vs SD vs PD)

- Baseline metastases: liver (+/- other visceral or non-visceral metastases) vs lymph node metastases only
- PDL1: high \geq 25% vs low \leq 25%

No formal comparisons will be performed between the subgroups.

Time-to-event analyses

Time-to-event of AESI and imAE:

Time-to-onset of AESI/imAE (by AESI/imAE category) and time-to-intervention with steroids, immunosuppressants and/or hormone replacement therapy to treat an AESI/imAE will be defined as time from first dose of durvalumab +/- tremelimumab to first onset of the event.

Time-to-event (TTE) is defined in months as follows:

TTE (months) = (Date of event or censoring–Date first dose of durvalumab [durvalumab + tremelimumab for the combinations modules]+1)/(365.25/12)

Time-to-resolution (TTR) of an AESI/imAE type is defined as the time from the first onset of an AESI/imAE type to the resolution of the AESI/imAE type. TTR is defined in months as follows:

TTR (months) = (Date of AESI/imAE resolution or censoring–Date of AESI/imAE onset+1)/(365.25/12)

Analysis of TTR will only include patients who have experienced an AESI/imAE.

The distribution of TTE and TTR times will be estimated using the Kaplan-Meier method (Kaplan and Meier 1958) and summarised using the median, twenty-fifth and seventy-fifth percentiles. TTE and TTR of imAE of NCI CTCAE grade >=3 will also be produced.

Deaths

A summary of deaths will present number (n) and percentage (%) of patients for the following categories:

- Total number of deaths (including deaths occurring within 90 days after last dose of study medication and deaths occurring after the 90 days post dosing window)
- Death related to disease under investigation ONLY, as determined by investigator (including deaths occurring within 90 days after last dose of study medication and deaths occurring after the 90 days post dosing window)
- TEAEs with outcome of death ONLY
- AEs with outcome of death ONLY and onset date falling after 90 days follow-up period
- Deaths related to disease under investigation, as determined by the investigator, and with TEAE with outcome of death
- Deaths related to disease under investigation, as determined by the investigator, and with AE with outcome of death and onset date falling after 90 days follow-up period
- Deaths that occurred 90 days after last dose, and unrelated to AE (ie no AE with outcome of death) or disease under investigation

- Patients with unknown reason for death
- Other deaths

Summary of long term tolerability

To assess long term tolerability, provided that there are a sufficient number of patients with events to warrant it (\geq 10 events), prevalence plots and cumulative incidence plots will be presented for each AESI category and for any other events considered important after review of the safety data.

A prevalence plot provides information on the extent to which the events may be an ongoing burden to patients. The prevalence at time t after first dose of study treatment is calculated as the number of patients experiencing the event divided by the number of patients receiving study treatment or in safety follow-up at time t; generally, t is categorised by each day after dosing. The prevalence will be plotted over time. Multiple occurrences of the same event are considered for each patient but a patient is only counted in the numerator whilst they are experiencing one of the occurrences of the event. The raw cumulative incidence is the actual probability that a patient will have experienced their first occurrence of the event by a given time point.

Treatment exposure

The following summaries related to study treatment will be produced for the SS:

- Total exposure, actual exposure, and total number of cycles received will be summarised separately for the initial treatment phase and the re-treatment phase. For the modules with combination therapy, those summaries will be carried out once for each drug separately and once for combination separately from monotherapy.
- Number of, reasons for, and duration of dose delays/interruptions of durvalumab and tremelimumab. Dose interruptions will be based on investigator initiated dosing decisions. In addition, interruptions due to AEs and due to reasons other than AEs will be summarized separately.
- Number of infusions received.
- Exposure over time will be plotted.

For patients on study treatment at the time of the OS analysis, the DCO date will be used to calculate exposure.

Subsequent Therapy

Subsequent therapies received will be summarized.

Laboratory assessments

Laboratory assessments are to be measured 90 days after last dose during the safety follow-up visit, per institutional care guidance only. Data obtained up until the 90 days following discontinuation of immunotherapy agents or until the initiation of the first subsequent therapy following discontinuation of treatment (whichever occurs first) will be used for reporting. This will more accurately depict laboratory toxicities attributable to study treatment only as a number of toxicities up to 90 days following discontinuation of immunotherapy agents are likely to be attributable to subsequent therapy.

A small selection of summaries of laboratory data may also be produced containing data from initiation of the first subsequent therapy following discontinuation of study treatment until 90 days following discontinuation of immunotherapy agents (i.e. summarising the laboratory data collected on patients taking subsequent therapy during the safety collection follow-up window post discontinuation of study treatment). These outputs will only be produced if the number of laboratory toxicities observed warrant the inclusion of such outputs for interpretational purposes. Any data post 90 days last dose will not be summarised.

Data summaries will be provided in International System (SI) of units.

For continuous laboratory assessments absolute value, change from baseline and percentage change from baseline will be summarised using descriptive statistics at each scheduled assessment time.

Shift tables for laboratory values by worst NCI CTCAE grade will be produced The laboratory parameters for which CTCAE grade shift outputs will be produced are:

- Haematology: Haemoglobin, Leukocytes, Lymphocytes (count, absolute), Neutrophils (count, absolute), Platelets.
- Clinical chemistry: ALT, AST, ALP, Total bilirubin, LDH, calcium, lipase, amylase, Sodium hypo and hyper, Potassium hypo and hyper, Creatinine, Urea nitrogen.

For the parameters with no CTCAE grading that are listed in the CSP, shift tables from baseline to worst value on-treatment will be provided (Haemoglobin, Erythrocytes, LDH, TSH, Urea nitrogen.

Urinalysis

Additional summaries will include a shift table for urinalysis (Hemoglobin, Leucocytes, Glucose, Ketones, Protein) comparing baseline value to maximum on-treatment value.

Liver Enzyme Elevations and Hy's law

The following summaries will include the number (%) of patients who have:

- Elevated ALT, AST, and Total bilirubin during the study
- ALT $\geq 3x \leq 5x$, $> 5x \leq 8x$, > 8x. > 10x and > 20x Upper Limit of Normal (ULN) during the study
- AST $\ge 3x \le 5x$, $\ge 5x \le 8x$, $\ge 8x$. $\ge 10x$ and $\ge 20x$ ULN during the study
- Total bilirubin $\ge 2x \le 3x$, $\ge 3x \le 5x$, $\ge 5x$ ULN during the study
- ALT or AST $\ge 3x \le 5x$, $\ge 5x \le 8x$, $\ge 8x$, $\ge 10x$ and $\ge 20x$ ULN during the study
- ALT or AST $\ge 3x$ ULN and Total bilirubin $\ge 2x$ ULN during the study

(Potential Hy's law): The onset date of ALT or AST elevation should be prior to or on the date of Total Bilirubin elevation

• Narratives will be provided in the CSR for patients who have ALT \geq 3x ULN plus Total bilirubin \geq 2x ULN or AST \geq 3x ULN plus Total bilirubin \geq 2x ULN at any visit.

Liver biochemistry test results over time for patients with elevated ALT or AST (ie \geq 3x ULN), and elevated Total bilirubin (ie \geq 2x ULN) (at any time) will be plotted. Individual

patient data where ALT or AST (ie \geq 3x ULN) plus Total bilirubin (ie \geq 2x ULN) are elevated at any time will be listed also.

Plots of ALT and AST vs. Total bilirubin will also be produced with reference lines at 3×ULN for ALT, AST, and 2×ULN for Total bilirubin. In each plot, Total bilirubin will be in the vertical axis.

Assessment of Thyrotoxicity

Thyroid function tests free T3 and free T4 are to be measured 90 days after last dose during the safety follow up visit, per institutional care guidance only. Data obtained up until the 90 days following discontinuation of immunotherapy agents or until the initiation of the first subsequent therapy following discontinuation of treatment (whichever occurs first) will be used for reporting.

For TSH absolute value and change from baseline will be summarised using descriptive statistics at each scheduled assessment time. Shift tables showing the change from baseline to maximum and from baseline to minimum will also be produced. Free T3 and free T4 will be listed only as they are to be tested only if clinically indicated.

ECGs

ECG data will not be summarized nor listed as only high/low values are reported in eCRF

Vital signs

Vital signs will summarised by study visit. Box plot of absolute values will be produced.

Physical examination

Individual physical examination data will not be listed. Physical examination abnormalities will be reported as AEs and included in AE listings.

ECOG performance status

Shift in Eastern Cooperative Oncology Group (ECOG) performance status (see appendix F of the CSP) will be summarised.

Other Safety Data

Data from positive pregnancy tests will be listed only. Safety findings reported in the CRF to support the monitoring and evaluation of imAEs will be listed.

